## SCHEMA

\*N=60-80 includes participants from Arm C who have services via the waitlist.

\*\*6-Month Outcome Survey also given to participants on Arms A and B that have lost contact with Penn Telegenetics before receiving genetic services

## **List of Abbreviations**

ENGAGE	ENGaging and Activating cancer survivors in GEnetic services
CCSS	Childhood Cancer Survivor Study
myLTFU	A HIPAA-compliant interface between participants, study investigators, and the CCSS Coordinating Center which allows direct messaging and web portal-based data collection
PCP	Primary Care Provider
SMN	Secondary Malignant Neoplasm
NCCN	National Comprehensive Cancer Network
GC	Genetic Counselor
FH	Family History
RCT	Randomized Controlled Trial

## **1.0 Background**

Germline cancer genetic testing has become a standard evidence-based practice, with established risk reduction and screening guidelines for genetic carriers (1-4). Yet, many at-risk patients do not have access to genetic services, leaving numerous genetic carriers unidentified and at increased risk of late diagnosis of cancers and inferior outcomes (5-9). Access to genetic specialists is limited in many areas in the U.S., requiring patients to travel long distances to referral centers or to work with primary care providers (PCPs) to order testing, presenting significant barriers to testing (9-12). Thus, innovative delivery models to increase uptake of genetic services and adherence to guidelines for genetic testing are needed to realize the benefits of Precision Medicine (8, 12-15).

Suboptimal access to genetic services is an acute problem for adolescent and young adult (AYA) cancer survivors, many of whom are at high risk for subsequent malignant neoplasms (SMN) because of cancer therapy or an inherited cancer predisposition (16, 17). A recent study revealed that 12% of survivors had a germline mutation in a cancer susceptibility gene (e.g. TP53, BRCA1/2) (18). National Comprehensive Cancer Network(NCCN) and Children's Oncology Group (COG) guidelines recommend survivors with personal (e.g. sarcoma) and/or family history of cancer be referred for genetic testing to implement appropriate surveillance or preventive measures (e.g. breast cancer surveillance or prophylactic mastectomy in women with TP53 or BRCA 1/2) (19,20). Yet, <15% of survivors have access to genetic services (21). Further, survivors and their PCPs are largely unaware of survivors' health risks and adherence to surveillance guidelines is low (22-26).

To address the gap in access to genetic services, this study will evaluate the effectiveness of an adapted model of remote delivery of genetic services to increase the uptake of recommended genetic assessment and testing in childhood cancer survivors. In a randomized study of remote telegenetic services delivered on-site at community oncology practices compared to usual care options for genetic services (e.g. travel to regional cancer program for counseling or testing) in adult patients who meet NCCN criteria for cancer genetic testing (PI:[name], clinicaltrials.gov NCT02517554), 77% of patients randomized to remote services had genetic counseling and 61% had genetic testing, as compared to 6% ( $p<0.001$ ) and 17% ( $p<0.001$ ) in the usual care arm (27). These data establish that providing remote genetic services can significantly increase uptake of genetic testing in patients in community practices. Yet, this on-site model requires collaboration with oncology practices and multi-level support within practices, which limits scalability for a nationally distributed population.

Remote telemedicine services by phone or videoconference could address gaps in access to recommended genetic testing. Genetic services are geographically limited, with the majority located in urban and/or academic centers. Some patients proceed with testing without a genetic provider (i.e. with their PCP). This has been shown to be associated with lower genetic knowledge and satisfaction, (28) and many at-risk patients do not proceed with testing at all (29-31). Remotely providing genetic services, as an alternative to in-person delivery, could address access barriers. Remote videoconference has been shown to be a highly effective alternative to in-person services in some areas (e.g. education, psychiatric services), (32, 33) but in areas such as cancer genetics data has been more limited, with no data reporting on extending services in the home, across a national population or in specifically childhood cancer survivors (34-45).

## **2.0 Purpose of Study**

As childhood cancer survivors receive care locally from PCPs, the ***in-home, collaborative PCP model*** is designed to increase access to genetic services and uptake of genetic testing in childhood cancer survivors. In this model, individual survivors can access remote telegenetic services and genetic counselors will partner with PCPs to order genetic testing. This approach of partnering with PCPs to increase compliance with guidelines has been successful in the North American cohort of childhood cancer survivors, the Childhood Cancer Survivor Study (CCSS). In the CCSS EMPOWER study (PI:[name], clinical trials.gov NCT01579552), 92% of survivors had a PCP who enrolled with their patient and women in the PCP-engaged intervention group were more likely (33.1% v. 17.6%, p=0.018) than controls to report a surveillance mammogram ordered by the PCP, providing support for our collaborative PCP model (46).

**ENGAGE (ENGaging and Activating cancer survivors in GEnetic services)** is a 3-arm randomized Hybrid 1 Effectiveness and Implementation study in 520 CCSS survivors to evaluate the effectiveness of our ***in-home, collaborative PCP model*** of remote telegenetic services to increase uptake of cancer genetic testing in childhood cancer survivors compared to usual care options for genetic testing.

**Specific Aim 1:** To evaluate the effectiveness of our ***in-home, collaborative PCP model*** of remote telegenetic services to increase uptake of genetic testing at 6 months as compared to usual care among childhood cancer survivors who meet criteria for cancer genetic testing. Our primary outcome will be a composite variable indicating whether a person had pre-test counseling or genetic testing.

**Specific Aim 2:** To evaluate the effectiveness of remote videoconferencing to provide greater increase in knowledge and decrease in distress and depression as compared to remote phone services (Aim 2a), to examine the moderators of patient outcomes with remote telegenetic services (Aim 2b), and to estimate intervention costs and incremental cost-effectiveness of the three study arms (Aim 2c).

**Specific Aim 3:** To conduct a multi-stakeholder, mixed-methods process evaluation to understand patient, provider and system factors associated with uptake of counseling and testing in our adapted ***in-home, collaborative PCP model*** and facilitators and barriers to uptake to provide recommendations for future implementation.

### **3.0 Methods**

#### **3.1 Subject Selection / Participant Characteristics**

All potential participants will be identified through the CCSS Coordinating Center. The CCSS Coordinating Center at St. Jude Children's Research Hospital is a multi-institutional cohort established in 1994 to evaluate the outcomes of childhood cancer survivors, and follows the outcomes of 24,335 childhood cancer survivors across the US (47). The CCSS Coordinating Center will use a combination of electronic (email/text), mailed, and phone-based recruitment methods to contact all potential participants. Recruitment materials will be sent to living CCSS participants to identify those who meet criteria for cancer genetic testing.

Potential subjects will include individuals who are:

- 18 years of age or older

- Able to understand and communicate in English
- Currently reside in the US
- CCSS survivors of the following primary cancers:
  - CNS tumor
  - Sarcoma (except Ewing sarcoma)
- CCSS participant with one or more subsequent malignant neoplasm (SMN)
- CCSS participant with any primary childhood cancer and a family history (FH) that meets NCCN criteria for genetic testing

Family history (FH) information will be assessed using existing CCSS data on the types of cancer the participant has reported in their family members, as well as the number of affected family members. The FH data was previously collected as part of the standard dataset for the CCSS Coordinating Center.

Exclusion criteria for this study include:

- Uncorrected or uncompensated speech defects that would lead to the participant being unable to communicate effectively with a medical provider
- Uncontrolled psychiatric/mental condition or severe physical, neurological or cognitive deficits rendering individual unable to understand study goals and tasks
- Participants who have already completed and received a clinically appropriate multi-gene panel genetic testing, or participants in the process of receiving genetic testing for hereditary cancer risk genes.

### **3.2 Enrollment Procedures**

The CCSS Coordinating Center will send an initial recruitment email (**Appendix A**) to all eligible CCSS participants. The CCSS Coordinating Center will then send a reminder email and text message via the myLTFU DatStat Connect portal to these participants that links the participant to the study's informational web page. Interested participants that follow this link will then be asked to log in and sign electronic informed consent (**Appendix B**) to enter the main home page on the myLTFU portal and join the study. Immediately following the informed consent, participants will be directed to complete an Eligibility Survey (**Appendix C**). Eligible participants will be directed to complete the Baseline Survey (T0) (**Appendix D**) through the myLTFU platform (see below in Section 3.3). Once eligible participants complete this Baseline Survey, they will be randomized to one of three arms (usual care control, remote telegenetic services by phone or by videoconferencing).

Mailed recruitment materials will also be used for participants that do not respond to the email recruitment methods. The CCSS Coordinating Center will complete follow-up phone calls for all participants that do not respond to email and mail recruitment materials.

### **3.3 Study Procedures and Measures**

#### **STUDY PROCEDURES**

This intervention will utilize a participant portal called myLTFU, a HIPAA-compliant interface between participants, study investigators, and the CCSS Coordinating Center. It allows direct and interactive messaging and web portal-based data collection, complementing already

established communication methods. The participant portal is accessible by computer, tablet, or smartphone. The application will allow participants to complete their assigned surveys, track their self-reported outcomes, view customized educational content, upload and download documents and pictures, and interact through secure chat with the study team.

Communication with participants will mostly take place via the DatStat Connect Platform, which allows pre-programmed messages and workflows to be activated by situational triggers.

#### RANDOMIZED STUDY PROCEDURES:

Once individuals have successfully completed the informed consent process, Eligibility Survey and Baseline (T0) Survey, the study steps will commence as follows:

##### 1. Randomization

Upon successful completion of informed consent and baseline (T0) survey, participants will be randomized into one of three potential study arms. Randomization assignments will be determined by a permuted block design and stratified by male/female/other. Study arms will consist of variations of methods of delivery for genetic counseling.

Once enrollment goals for Aim 1 are reached (120 completed baseline survey and sent randomization flyer), we will halt enrollment of Arm C. We will continue to enroll to Arms A and B to meet enrollment goals for Aim 2.

ARM	COUNSELING METHOD
ARM A	Remote Videoconference Telegenetics
ARM B	Remote Phone Telegenetics
ARM C	Usual Care

After randomization, participants will be sent information flyers (**Appendix E**) via the myLTU app that correspond to the appropriate arm to which they have been randomized. Flyers will include instructions for how to contact the Penn Telegenetics team to schedule their appointment (Arms A and B) or usual care options (Arm C) for obtaining genetic services (e.g. ask PCP or providers, use the National Society of Genetic Counselors website [www.nsgc.org](http://www.nsgc.org)).

Participants will be followed up with by a member of the research team to ensure they have received the flyers with the randomization assignment and information. Participants in all arms will be fully informed of how to initiate genetic services, and that it is their responsibility to do so.

##### 2. Pre-Test Counseling, Visit 1 (Remote Telegenetics Arms A and B)

Those who contact the Penn Telegenetics will be registered with the Penn Telegenetics Program, consistent with routine clinical care. They will be scheduled with a Penn Telegenetics Genetic Counselor according to their study arm. Participants in Arms A and B will be asked to complete a study survey following their pre-test counseling sessions, Visit 1 (T1) (**Appendix F**).

**ARM A: Remote telegenetic counseling by videoconference:** Those who contact Penn Telegenetics in Arm A will complete their pre-test counseling session (Visit 1) by videoconference, utilizing communication protocols and checklists adapted from related studies

**(Appendix G)** (50). Penn GCs are licensed in all U.S. states that require licensure to provide remote telegenetic services (49). Consistent with standard clinical practice, GCs will review personal and FH, the risks, benefits and limitations of genetic testing, testing options based on their personal and FH (e.g. *TP53* testing or a panel of cancer susceptibility genes) and the costs associated with genetic testing. If the participant consents, this session will be recorded for research and training purposes.

**Videoconferencing Technology platforms:** Participants will be provided links to download secure, HIPAA compliant, videoconferencing software on their home computer or device. The Penn Telegenetics team provides back-up systems if one platform is not able to launch or fails to maintain connectivity. In our communication protocols, if videoconference technology fails, GCs will convert the session to phone.

**ARM B: Remote telegenetic counseling by phone:** Participants will complete their pre-test counseling (Visit 1) session by phone with a Penn Telegenetic Counselor (GC) utilizing communication protocols and checklists adapted from related studies (Appendix G) (48). The remainder of procedures for pre-test counseling are as described above for Arm A. If the participant consents, this session will be recorded for research and training purposes.

**ARM C: Usual Care Arm:** Participants in the usual care arm will receive usual care services depending on which referral method they choose and if they initiate services. As below, after the 6-Month Outcome Survey, if they have not had genetic services through usual care they will be offered services and re-randomized to Arm A/B in a waitlist design.

### 3. Genetic Testing

**ARMS A and B:** If patients on Arms A and B elect to proceed with genetic testing, they will be asked to provide their PCP's/ or other provider's (usual source of care or a local health care provider of their choice) contact information. A licensed physician is required to order genetic testing in most states. If [name] or [name] has licensure in the residing state, they will be the ordering physician if no PCP/ provider has been identified. The Penn Telegenetics Team will contact the patient's PCP/provider and their practice to inform them that their patient is a candidate for remote genetic services and the Penn Telegenetic counselors can provide counseling and facilitate testing through a collaborative relationship with the patient's provider. The PCP/provider would need to agree to be the ordering provider for the genetic testing and register with the Penn Telegenetics Program, a model that has been successful in our current clinical program. PCPs/providers will provide their credentials and contact information, so that the GC can collaborate with the provider to facilitate testing. Practice staff will be permitted to complete the PCP/provider registration on behalf of the provider. Once the PCP/provider has registered and agreed to support testing in their patient, the Penn GC will collaborate with the patient and provider/practice to arrange for sample collection, and provide support for insurance coverage. The registered PCP/provider will receive a chart note summarizing the pre-test counseling visit and testing ordered.

**ARM C:** Participants in the usual care arm will receive usual care services depending on which referral method they choose and if they initiate services. As below, after the 6-Month Outcome Survey, if they have not had genetic services through usual care they will be offered services and re-randomized to Arm A/B in a waitlist design.

**Genetic Testing in all arms** will be clinical cancer genetic testing through standard clinical commercial labs, consistent with real-world practice and as indicated based on their personal

and family history. Most testing will be covered by insurance. Consistent with our experience in community patients in the Penn Telegenetics Program, we expect the majority of participants to have coverage. For those who do not, GCs can use commercial lab financial assistance programs or identify the lowest possible self-pay options, consistent with their current practice. For example, there are currently several labs that offer genetic testing or panels for  $\leq \$250$ . This information will be provided in the study flyers, so that it is accessible to all participants regardless of arm.

#### 4. Genetic Testing Result Disclosure, Visit 2 (Remote Telegenetics Arms)

**ARM A: Remote telegenetic counseling by videoconference:** The Penn GC will share results with the patient by videoconference at a scheduled visit. The Penn GC will provide the patient's provider with a chart note, summarizing the results and associated implications and cancer risk estimates, as well as standard risk reducing or screening strategies and implications for relatives. Penn GCs will be available to answer PCP/provider questions (by email or phone) and facilitate referral to regional clinical expertise centers as indicated. Patients will be recommended to follow-up with their PCP/provider to implement any screening and medical (including risk reduction) recommendations. If the participant consents, this session will be recorded for research and training purposes.

**ARM B: Remote telegenetic counseling by phone:** The Penn GC will share results with the patient by phone at a scheduled visit. The remainder of procedures for post-test counseling are as described above for Arm A. If the participant consents, this session will be recorded for research and training purposes.

Following the completion of the disclosure session, participants on Arms A and B will also be asked to complete a study survey (T2) (**Appendix H**).

#### 5. Completion of Primary Outcome 6-Month Status Survey (Usual Care Arm & Certain Remote Telegenetics Arms Participants, **Appendix I1**)

Participants on the usual care arm will be contacted at the 6-month timepoint (6-months post randomization) to assess uptake of genetic services. Participants on Arms A and B that have not completed genetic counseling or testing will also be contacted at the 6-month timepoint to assess uptake of genetic services through the 6-Month Status Survey. Those who have had genetic testing will be asked to provide authorization for the study team to obtain a copy of their genetic test result for the purpose of research (**Appendix I2**).

Participants on Arm C that have not had genetic testing at 6 months will be offered telegenetic services (waitlist design, see **Study Schema**). This option will not be shared at enrollment. Rather, they will be told that after they complete the 6-Month Status Survey, we will review again genetic testing options with them.

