## OUTCOMES AND MEASURES

Table 1. Effectiveness outcomes and measures			
CONSTRUCT	T0	T1	T2-T4
Moderators of patient outcomes			
Sociodemographics	X		
Cancer history	X		
Family history	X		
Health literacy	X		
Comfort with technology	X		
Self-efficacy	X		
Financial Wellness	X		
COVID Impact	X		X
Outcomes			
Uptake counseling, testing, identification carriers at 6 months* (Telegenetics records for Arms A/B & the 6-Month Status Survey in Arm C)			
Understanding of Genetic Information**			
Test result recall			X
Knowledge of genetic disease	X	X	X
Perceived risk	X	X	X
Reactions to genetic information**			
Anxiety and Depression	X	X	X
Cancer specific distress	X	X	X
Satisfaction with genetic services and telemedicine		X	X
Behavioral use of genetic information**			
Performance of behaviors	X		X
Cost (patient and system)**		X	X

\*Aim 1; \*\*Aim 2; T0=baseline (within 30 days of visit 1, can accept within 45 days. beyond that it needs to be updated), waitlist usual care participants will need to complete a new baseline, T0b; T1=survey post pre-test counseling, Visit 1 (ideally collect 1-3 days and up to 7 days. accept up to 14 days but from 7-14 days we may elect to drop and impute). T2=survey immediately post genetic testing disclosure (same timing as T1); T3/T4 survey=6/12-month post genetic testing disclosure (ideally get within 14 days of 6/12 month mark but accept within 60 days of 6 month or 12 month mark)

The T0-T4 patient surveys for the RCT will be completed through a secure website, linked through the myLTFU platform. The 6-Month Outcome Survey will be administered by phone. If the phone survey cannot be completed, the survey will be offered self-administered through the myLTFU platform.

Effectiveness Outcomes (Aims 1 and 2):

**1) Uptake of counseling, testing and identification of carriers at 6 months** (Aim 1): This information will be obtained through study records for Arms A and B (intervention arms) and the 6-Month Outcome Survey among nonresponders in Arm A and B (e.g. those who did not contact Penn Telegenetics or did not complete visit 1 or visit 2) and in Arm C (usual care). The outcome survey will query completion of each outcome, date, and provider and will explore barriers and reasons for no uptake (Appendix I).

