**Missing data:** We do not expect substantial missing data, although there may be loss to follow-up over time. For the primary outcomes, we will assume that those lost to follow-up did not have pre-test counseling or testing (i.e. failures under the intention-to-treat paradigm). Data from our community practice stakeholder interviews suggests this is reasonable since many patients do not get genetic services even when referred. In secondary analyses, we will account for missing data using the multiple imputation technique of Raghunathan with 25 imputed datasets.(81) We will contrast the results obtained through imputation and those obtained from complete case analyses to study if missing data bias could be substantially affecting our inferences.

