### **5.1 Payment to subjects:**

Participants will receive a gift card code in the defined amount for the completion of the following surveys in the randomized trial:

- Baseline (T0) Survey: \$25
- Pre-Test Counseling Session Session (T1) Survey (Arms A & B): \$25
- Disclosure Counseling Session (T2) Survey (Arms A & B): \$25
- 6-Month Follow Up (T3) Survey (Arms A & B): \$30
- 6-Month Outcome Survey (Arm C only): \$75
- 12-Month Follow Up (T4) Survey (Arms A & B): \$30

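### The plan is inconsistent about which Arm A/B participants get the 6-month outcome survey and pays only Arm C for it; the exposure is mainly in the testing, carrier and cost-effectiveness results

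*Combined protocol and SAP*

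**What the plan says.** All of Arm C is contacted at 6 months (section 3.3, item 5). For Arms A and B, the current text describes the survey population in four places:

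- Schema footnote: "participants on Arms A and B that have lost contact with Penn Telegenetics before receiving genetic services".
- Section 3.3, item 5: "Participants on Arms A and B that have not completed genetic counseling or testing will also be contacted at the 6-month timepoint".
- Table 1, uptake row: "Telegenetics records for Arms A/B" and "the 6-Month Status Survey in Arm C". No A/B survey is named.
- Outcome text below Table 1: study records, plus the survey among A/B nonresponders, for example "those who did not contact Penn Telegenetics or did not complete visit 1 or visit 2".

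The instrument is called both a Status Survey and an Outcome Survey. Both names point to Appendix I1, so I treat them as one survey. The payment list in section 5.1 has the entry "6-Month Outcome Survey (Arm C only" at $75 and shows no A/B payment for it. For missing primary outcomes, section 4.0 states: "we will assume that those lost to follow-up did not have pre-test counseling or testing".

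**The concern.** This survey sets the primary outcome in Arm C and is the only route by which an outside service could be counted in Arms A and B. It asks about completion, date and provider, so outside services appear meant to count. If staff follow a narrow rule, a service obtained locally by an A/B participant goes unrecorded, while the same service in Arm C is asked about directly.

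The group most at risk is A/B participants who were counselled by the study but tested elsewhere. That route is plausible. Section 3.3, item 3 generally needs a local provider to agree to order the test and to register with the telegenetics program, and such a provider could order outside it. These people already count for the composite through Visit 1. They would be lost to the testing and carrier secondaries and to both cost-effectiveness denominators (survivors tested within 6 months, mutations detected).

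Paying one group for the survey and scoring non-response as failure also invites response that differs by arm.

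**Working it through.** **1. The plan's own figure.** Inputs from section 4.0: 120 versus 240 participants, uptake 17% (4/24) versus 53% (29/55), two-sided alpha 1%, Fisher's exact test. The normal approximation gives power 0.999998, and full enumeration of the exact test gives 0.999995. The stated figure of more than 99% reproduces.

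**2. The rules side by side.** Is an outside service found by the survey for each type of A/B participant?

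| A/B participant | Schema footnote | Table 1 | Item 5, neither service | Item 5, not both | Outcome text |
|---|---|---|---|---|---|
| Never contacted the program, served locally | Doubtful | No | Yes | Yes | Yes |
| Lost contact before Visit 1, served locally | Yes | No | Yes | Yes | Yes |
| Visit 1 done, tested elsewhere | No | No | No | Yes | Yes |

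The first two rows decide the composite. Both readings of item 5 and the outcome text cover them. The third row affects testing and carriers only, and only the outcome text covers it without depending on how an ambiguous word is read.

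**3. Records-only worst case.** Points missed = (share of A/B without the study service) × q, where q is outside uptake among them.

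- Share without counselling: 1 − 0.77 = 23% (remote arm of the earlier trial, section 1.0). I take this as the share without either service.
- Share without testing: 1 − 0.61 = 39% (section 1.0) to 1 − 0.53 = 47% (section 4.0).
- q: assumed 6% to 17%, the usual-care counselling and testing rates in section 1.0. The documents give no rate for A/B participants who do not use the study service.

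Composite: 0.23 × 0.06 = 1.4 points; 0.23 × 0.17 = 3.9 points.
Testing: 0.39 × 0.06 = 2.3 and 0.47 × 0.06 = 2.8 points; 0.39 × 0.17 = 6.6 and 0.47 × 0.17 = 8.0 points.
The planned difference is 53 − 17 = 36 points.

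**4. Net effect once Arm C non-response is included.** Let P be recorded A/B uptake, c true Arm C uptake, r survey response among A/B participants without a study service, and rC survey response in Arm C. With missing scored as failure:

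- Observed A/B = P + (1 − P)·q·r; true A/B = P + (1 − P)·q
- Observed C = c·rC; true C = c
- Shift in the difference = c(1 − rC) − (1 − P)·q·(1 − r)

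P = 0.53 and c = 0.17 come from section 4.0. rC = 0.85, q and r are illustrative assumptions. The Arm C term is 0.17 × 0.15 = +2.6 points. For q = 17% and r = 0, the A/B term is 0.47 × 0.17 = 8.0 points, so the shift is −5.4.

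| q | r = 0 | r = 40% | r = 85% |
|---|---|---|---|
| 0% | +2.6 | +2.6 | +2.6 |
| 6% | −0.3 | +0.9 | +2.1 |
| 10% | −2.2 | −0.3 | +1.8 |
| 17% | −5.4 | −2.2 | +1.4 |

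Power at the observed rates stays above 99% in every cell.

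**The case against.** The case for leaving this alone has five parts.

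- **Four incompatible rules.** A reader might infer this, but the documents do not support it. Table 1's entry is a short label, and the numbered text below it expands that label to include A/B nonresponders. Item 5, read as lacking either service, nearly matches that text. What remains is a label, a narrower footnote and an ambiguous conjunction. The inconsistency is still real, because the footnote and the label cannot both agree with the outcome text.
- **The primary result is at risk.** This does not follow either. Item 5 and the outcome text both survey every A/B participant with no study service, and anyone with Visit 1 is already a success by records.
- **The bias runs against A/B.** That holds for missed A/B services taken alone. Arm C depends wholly on a survey with missing scored as failure, which favours A/B.
- **Missing data are already handled.** Section 4.0 plans multiple imputation and complete-case analyses. These help when a surveyed person does not respond. They do not help if a person never surveyed is entered as an observed failure.
- **Equal payment has a drawback.** By result disclosure, an A/B participant completing T1 and T2 has received $25 + $25 = $50 for them. Paying $75 to those without disclosure would reward non-uptake more. This stands, and is why the fix offers an alternative to equal payment.

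**Conclusion.** The inconsistency holds and should be corrected before analysis. It bears mainly on the testing and carrier secondaries and the cost-effectiveness denominators. The composite is affected only if Table 1 or the schema footnote governs practice, or if unpaid A/B participants respond less often.

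The sizes, 1–4 points for the composite and 2–8 points for testing, are a records-only ceiling at pilot rates and an assumed 6–17% outside uptake. The 17% rests on 4/24 (exact 95% interval about 5–37%). Applying it to people who were counselled and chose to defer testing may be generous. In the other direction, the 2023 amendment note implies that more A/B participants will lack disclosure than the pilot rates suggest, and the testing figure would rise in proportion.

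The net direction is undetermined: the illustrative scenarios run from about −5 to +3 points. The primary test is not threatened.

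**What to change.** 1. Make the outcome text below Table 1 the single rule and repeat it in the schema footnote, Table 1 and section 3.3, item 5: every A/B participant without a recorded study result disclosure at 6 months gets the survey.
2. State that a service counts whatever its source, in every arm.
3. Reconcile section 5.1 so that the incentive does not differ by arm among those asked to complete the survey. If it stays different, report 6-month survey response by arm and add a sensitivity analysis for differential non-response.
4. If follow-up has finished, state which rule was used.

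Items 1 and 2 cost wording only, because the outcome text already plans these contacts and section 3.3 already gives one mode of administration (phone, then the portal) without distinguishing arms.

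Equal payment at $75 costs more than a count based on the 240 A/B participants in the Aim 1 power calculation would suggest, because A/B enrolment continues after Arm C closes: 520 − 120 = 400.

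- At 39–47% without disclosure: 400 × 0.39 = 156 and 400 × 0.47 = 188 surveys, or $11,700 to $14,100.
- Under the 2023 amendment note (60–80 Visit 2 completions per arm, so at most 160): at least 400 − 160 = 240 surveys, or $18,000 or more.

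Both figures assume that about 400 enrol in Arms A and B and that everyone asked responds.
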